Official Title: Develop the Mini-flipped Game-based Learning Strategies in Modified Mediterranean Diet Interventions for Eating Behavior and Cognitive Performance Among Older Adults in the Community

NCT number: NCT04788446

Document date: July 6th, 2021

Study Protocol

Background

The world is facing an aging population and the number of people with mild cognitive impairment and dementia is increasing, causing a huge burden of medical costs for individuals, families and society. Previous studies have shown that the Mediterranean Diet (MD) can prevent cognitive decline, but older adults are less likely to follow the Mediterranean Diet and have little knowledge about the risk of dementia and protective factors of the diet. The Game-based learning can enhance the learning effectiveness and motivation of the elderly. In this study, the content of the Asian version of the Mediterranean Diet Pyramid and the local food materials from Taiwan will be integrated into the nutritional health education with game strategies of the Modified Mediterranean diet.

Objective

The purpose of this study was to explore the effect of developing Mini-flipped Game-based learning Strategies in Modified Mediterranean diet learning intervention to promote eating behavior and cognitive function of elderly people in community.

Methods

1. Study design:

This study was designed as a cluster randomized controlled trial. First, six communities were selected from Taipei Beitou District, and then randomly assigned to the experimental group and the control group by computer. A total of 80 elderly people were included in this study. The inclusion conditions of the research subjects include: (1) the elderly over 65 years old; (2) Those who have no visual or hearing impairment or mental impairment and can communicate in Chinese and Taiwanese; (3) Those who are willing to participate in the research and fill in the voluntary consent form. Exclusion criteria were :(1) diagnosed with cognitive dysfunction, brain injury and loss

of consciousness for more than 30 minutes or other central nervous system diseases; (2) Suffering from serious diseases, such as organ failure of heart, liver and lung, end-stage kidney disease, general paralysis, end-stage cancer or chemotherapy, and diagnosis of mental diseases.

2. Research tools:

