The measurements included a demographic information, the Mediterranean Diet score, the Chinese version of the Montreal Cognitive Assessment Scale, the Chinese version of the Cognitive Failures Questionnaire, the Nutrition Knowledge for the Elderly Scale, the Chinese version Pittsburgh Sleep Quality Index, and the Center for Epidemiological Studies Depression Scale. The study was a single-blind design and was measured at the pre-test (week 0) and post-test (week 8).

3. Intervention approaches:

The experimental group used a Mini-flipped game-based learning strategies in modified Mediterranean diet learning intervention, and the duration of the intervention was 8 weeks, with 40-minute Mini-flipped game-based learning strategies in modified Mediterranean diet learning each week, which the content included: the relationship between the Mediterranean diet and dementia, knowledge of the Mediterranean diet, and how to incorporate local ingredients into the Mediterranean diet. The control group was given a leaflet on balanced diet and nutrition in elderly by the Health Promotion Administration.

Statistical Analysis Plan

SPSS25 software was used for data analysis. The scores of socio demography, eating behavior, cognitive function, nutritional knowledge, depression and sleep in the two groups were described by the descriptive statistical methods, such as percentage, mean and standard difference. Chi-square test (χ^2 test), Fisher's exact test or independent t-test were used to test the homogeneity of the two groups of data. In this study, generalized estimating equations (GEE) were used to measure the differences in dietary behavior, cognitive function and nutritional knowledge between the two groups before and after intervention. Two-tail test was used for all statistical analyses, and the significance level $\alpha=0.05$ was set.

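### The GEE names no baseline conditioning, working correlation or subject unit, so baseline-related dropout that differs by arm could bias the group-by-time estimate

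*Combined protocol and SAP*

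**What the plan says.** In the Statistical Analysis Plan, the only method for comparing the arms over time is this: "generalized estimating equations (GEE) were used to measure the differences in dietary behavior, cognitive function and nutritional knowledge between the two groups". Chi-square, Fisher and t-tests are listed, but only to check that the groups are alike. The plan does not state a working correlation, the model terms, whether the GEE subject is the person or the community, any use of the week-0 score as covariate, or how missing week-8 scores are handled.

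Methods, section 2, gives two measurements, at weeks 0 and 8. Methods, section 1, describes a cluster randomized trial: "six communities were selected from Taipei Beitou District", and "A total of 80 elderly people were included in this study". Methods, section 3, sets out unequal demands on the arms. The experimental arm has eight weeks of intervention, "with 40-minute Mini-flipped game-based learning strategies in modified Mediterranean diet learning each week"; the control arm receives a leaflet.

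**The concern.** A two-time-point GEE with group, time and group-by-time terms uses everyone at week 0 but only the retained people at week 8. How far it corrects for who was lost depends on the pre-post correlation it uses, and the plan leaves that open. Suppose lower scorers leave the session arm and the leaflet arm loses people without regard to score. On a scale where higher is better, the session arm's week-8 mean then rises with no true effect. Analysing unadjusted change in completers gives a bias of the opposite sign. The size and even the sign of the error could therefore turn on a setting that the plan does not fix, although the week-0 score needed to avoid it is already collected.

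**Working it through.** **Inputs from the documents:** GEE as the method, two time points, 80 people, six communities. The sample size of 80 comes without a derivation, so there is no planned figure to reproduce.

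**Assumptions (not in the documents):** no true effect; normal scores with baseline SD 1; pre-post correlation ρ of 0.5 to 0.8; week-8 SD k times baseline; 40 people per arm. Session-arm dropout is 40%, 30% or 20% below the baseline median and 10% above it. Leaflet-arm dropout is 5%, unrelated to score.

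**Step 1: baseline shift among those retained.** The upper and lower halves of a standard normal have means ±0.798. With retention p_hi above and p_lo below the median, δ = 0.798 × (p_hi − p_lo)/(p_hi + p_lo):
- 40%/10%: 0.798 × (0.9 − 0.6)/1.5 = 0.160
- 30%/10%: 0.798 × (0.9 − 0.7)/1.6 = 0.100
- 20%/10%: 0.798 × (0.9 − 0.8)/1.7 = 0.047

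In the leaflet arm δ = 0.

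**Step 2: bias.** With persons as subjects, the GEE corrects the retained week-8 mean by r × δ, where r is the working correlation. The correct amount is ρkδ, so the bias is (ρk − r)δ.

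With independence, r = 0. With k = 1 the bias is ρδ. For unadjusted change in completers it is (ρ − 1)δ.

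| Session-arm dropout | Independence GEE, ρ = 0.5 / 0.6 / 0.8 | Completer change, ρ = 0.5 / 0.6 / 0.8 |
|---|---|---|
| 40%/10% | +0.080 / +0.096 / +0.128 | −0.080 / −0.064 / −0.032 |
| 30%/10% | +0.050 / +0.060 / +0.080 | −0.050 / −0.040 / −0.020 |
| 20%/10% | +0.023 / +0.028 / +0.038 | −0.023 / −0.019 / −0.009 |

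*Person-level exchangeable.* Here r ≈ ρk/φ with φ = (1 + k²)/2. For k = 1, r = ρ and the bias is about 0.00. For k = 1.5 and ρ = 0.6, φ = 1.625 and r = 0.9/1.625 = 0.554. Under 40%/10% the bias is (0.9 − 0.554) × 0.160 = 0.055; simulation gives about 0.05. A random-intercept mixed model with one residual variance has the same covariance form and the same weakness.

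*Community-level exchangeable.* A community of 13 people has 26 scores and 26 × 25/2 = 325 pairs, of which only 13 are within a person. With no community effect the averaged correlation is 13 × 0.6/325 = 0.024, so almost nothing is corrected. Simulation under 40%/10% v 5% gave 0.09-0.11 SD, much the same as independence.

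*Week-8 score with week-0 covariate.* The fitted slope estimates ρk, so the bias is 0.00. Simulation agreed in the baseline-dependent dropout scenarios run, to within about 0.01 SD.

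**Step 3: precision (ρ = 0.6, 40 per arm, clustering ignored).** With no dropout, the SE for change is √(2 × 0.4 × 2/40) = 0.200; with baseline as covariate it is √((1 − 0.36) × 2/40) = 0.179. Simulation gave 0.201 v 0.181, about 10% lower. Under 40%/10% v 5%, the simulated SE was 0.199 with the covariate, 0.217 for exchangeable GEE (1 − 0.199/0.217 = 8%) and 0.226 for independence (1 − 0.199/0.226 = 12%).

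**The case against.** The plan never specifies independence. With persons as subjects and equal variances, an exchangeable structure all but removes the bias, so GEE itself is not shown to be the wrong method. That stands, and it is why the fix does not require GEE to be dropped.

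A reader might infer that GEE is valid here only if dropout is completely at random. That is too strict. In simulation, dropout that depended on arm alone (25% v 10%) gave no bias. Neither did dropout related to baseline in the same way in both arms. Bias needs dropout that is related to baseline and differently so by arm.

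A reader might also infer that the result will favour the intervention. The documents do not support a direction. People with diagnosed cognitive dysfunction or serious illness are excluded, which narrows the frail tail. Missing a session is not the same as missing the week-8 measurement. The Background also says that game-based learning can raise motivation, so the session arm might retain people better.

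Every dropout figure is assumed. The mildest case, 0.02-0.04 SD, is under a fifth of the standard error (0.038/0.226 = 0.17). With a logistic dropout model at 80 people, independence GEE rejected a true null 7.1% of the time under 20% baseline-related v 10% random dropout, against 6.3% when dropout was random. It reached 13.9% only when the arms lost people in opposite directions.

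What the objection does not remove is that the protection rests on three unstated conditions: a suitable working correlation, the person as subject, and similar variances at both times. In a trial randomized by community, the community is a natural choice of subject.

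**Conclusion.** The point holds as a conditional risk. Under the assumed dropout and correlations of 0.5 to 0.8, the bias with independence is about +0.02 to +0.13 SD. With person-level exchangeable correlation it is about 0.00 SD if variances are equal, and about 0.05 SD in the heaviest dropout case if the week-8 SD is 1.5 times baseline. The documents give no dropout rate, pre-post correlation or SD, so neither the occurrence nor the sign of the bias is established.

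The case for change does not rest on dropout alone: conditioning on the baseline score gains about 10% in standard error with complete data. The precision figures assume correlation 0.6 and ignore clustering by community.

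**What to change.** - Make the main comparison the week-8 score between arms with the week-0 score as covariate, in GEE or a mixed model, allowing for community. State the model terms, subject unit and working correlation.
- If both time points are modelled jointly, use an unstructured person-level covariance with a separate variance at each time, not independence or a single-variance random intercept. With two time points, an unstructured GEE working correlation still holds only one correlation, and with a common scale it does not free the variances. This option therefore points to a mixed model.
- Report week-8 dropout by arm and by baseline score.

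The cost is SAP wording and a small amount of analysis; no new data are needed. The downsides are that people without a week-8 score contribute only through the baseline-conditional model, and that a linear relation with baseline is assumed. Conditioning on baseline does not protect against dropout that depends on the unseen week-8 score itself. Valid inference with only six communities is a separate matter that this change does not settle.
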